Parenting interventions in conflict-affected settings have often assumed that poor parenting stems mainly from a lack of knowledge or skills. However, research shows that caregiver stress and mental health challenges—driven by war exposure and daily stressors—play a central role in sub-optimal parenting. The family stress model highlights how caregiver wellbeing mediates the impact of conflict on parenting, with negative consequences for children’s psychosocial health. Studies further show that caregivers themselves are frequently perpetrators of abuse in emergencies, and that caregiver mental health is directly linked to child mental health outcomes among conflict-affected and displaced populations.

To address these interconnected factors, War Child developed *BeThere*, a nine-session preventive group intervention for caregivers of children aged 3–14 affected by armed conflict and forced migration. Grounded in the family stress model, the program combines parenting support with a strong focus on caregiver mental health. The first four sessions emphasize caregiver mental health and stress management, followed by sessions on positive parenting in adversity, with a final review session. Through this dual focus—building evidence-based parenting skills and strengthening caregiver mental health—*BeThere* seeks to improve both parenting practices and child wellbeing.

8. Objectives

The overall objective of this study is to evaluate the effectiveness of BeThere for improving parenting behaviors and child wellbeing in Bor County, South Sudan. The research objectives are as follows:

Primary Objectives

1. To evaluate the effectiveness of the BeThere intervention in improving parenting among participating caregivers in a fully-powered trial in South Sudan
2. To evaluate the effects of the BeThere intervention on participating caregivers’ children using child-reported outcomes among a subsample of children aged 7-14.
3. To estimate the indirect effect of the BeThere intervention via caregiver wellbeing, caregiver distress, caregiver stress, and parenting on child wellbeing.

Secondary Objective

4. To assess the effect of group cohesion among beneficiaries in the BeThere intervention group on caregiver wellbeing and distress

SECTION 3: STUDY METHODS

9. Trial design

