Randomization followed a participatory procedure successfully implemented in prior RCTs. At baseline, after completing questionnaires, one caregiver per family drew a piece of colored paper (yellow or green) from an opaque bag with equal distribution, ensuring balance across groups. One of the chiefs in each community then flipped a coin to determine which color corresponded to *BeThere* versus waitlist control. This process was repeated in each study community to maintain equal allocation across sites. The two-step method was designed to enhance transparency and community acceptance; previous studies using this approach showed no baseline imbalances and high follow-up rates in both arms.

Within families, a single index child aged 3–14 was randomly selected using a die-rolling procedure, proportionate to the number of eligible children. If the selected child was 7–14 years old, and both caregiver and child provided consent/assent, the child completed their own assessments at baseline, endline, and follow-up. Group assignments and index child selections were recorded in a master list maintained securely in War Child offices, with access restricted to the scientific and research coordinators.

11. Sample size

Sample size calculations were conducted using a joint significance estimator for indirect effects. Assuming a two-sided alpha of 0.05, an intervention–mediator error correlation of 0.2, mediator SD of 0.2, and error SD of 0.5, a sample of 425 caregivers per arm was sufficient to detect a mean difference of 0.4. Allowing for 10% attrition, the study aimed to enroll 960 caregivers (at least 480 families) and 400 index children across 40 intervention groups, providing adequate power to test multiple mediator models. In the end, we enrolled 956 caregivers and 328 index children.

12. Framework

The objective of the study has a superiority hypothesis testing framework. It aims to show the superiority of BeThere relative to the waitlist control condition on primary and secondary outcomes. In addition, through mediation analyses, this study aims to identify the mechanisms through which BeThere exerts an effect on child wellbeing.

13. Statistical interim analyses and stopping guidance

No interim analyses of study outcomes were planned or conducted. The Data Safety Management Committee reviewed adverse events throughout the study implementation and were responsible for determining whether any actions were required to reduce risk to study participants.

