- **Parenting (caregiver-reported; primary outcome(s)):** Total score on a 24-item parenting scale developed to assess change in parenting. The total score combines subscales assessing parental warmth and sensitivity (17 items) and harsh parenting (six items). Parenting was assessed at baseline, endline, and follow up. Caregiver-reported parenting at endline will be considered the primary effectiveness outcome for the study.

Secondary outcomes

- **Parenting (child-reported; secondary outcome):** Total score on a 24-item parenting scale developed to assess change in parenting. The total score combines subscales assessing parental warmth and sensitivity (17 items) and harsh parenting (6 items). Child-reported parenting was assessed at baseline, endline, and follow up. The child does not report separately on multiple caregivers.
- **Caregiver psychological distress (secondary outcome):** Total score on the 10-item Kessler Psychological Distress scale. Caregiver psychological distress was assessed at baseline, midline, endline, and follow up.
- **Caregiver stress (secondary outcome):** Total score on the 18-item caregiver stress measure developed by War Child. Caregiver stress was assessed at baseline, midline, endline, and follow up.
- **Caregiver psychosocial wellbeing (secondary outcome):** Total score on the 14-item Warwick-Edinburgh Mental Wellbeing Scale. Caregiver psychosocial wellbeing was assessed at baseline, midline, endline, and follow up.
- **Child psychosocial wellbeing (caregiver-reported; secondary outcome):** Total score on the modified 25-item Kiddy-KINDL for Parents measure evaluating wellbeing specifically among the index child. A modified version of the KINDL for Parents was used that combines the Kiddy-KINDL (3-6 years) and Kid-KINDL (7-13 years) into a single measure. Child wellbeing was assessed at baseline, endline, and follow up.
- **Child psychosocial wellbeing (child-reported; secondary outcome):** Total score on the modified 25-item Kid-KINDL for Children. This measure is completed by index children ages 7-14 years only. Child psychosocial wellbeing was assessed at baseline, endline, and follow up.

Mediators

- **Group cohesion:** Total score on the 7-item Group Cohesiveness Scale. Group cohesion was assessed at midline, endline, and follow up.

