Mediation Analyses

Estimate indirect effect of BeThere intervention on child wellbeing via caregiver wellbeing, caregiver distress, caregiver stress, and parenting.

Single mediator models. We will test for the effect of the BeThere intervention on each one of the multiple continuous mediators with the use of linear regression models. We chose a priori a p-value of lower than 0.15 to select the appropriate mediators to include in our final mediation analysis. We will test independence by examining partial correlations between our mediators after accounting for treatment allocation.

Full Structural Model. We will estimate a parametric structural equation model (sem package in Stata version 16.0 [StataCorp]) to estimate the total effect, the natural indirect effects (NIE), and natural direct effects (NDE) of Bethere on child wellbeing via caregiver wellbeing, caregiver distress, caregiver stress, and parenting. The NDE represented the effect of BeThere on Child Psychosocial Wellbeing (caregiver report) that was independent of caregiver wellbeing, caregiver distress, caregiver stress, and parenting. The NIE represents the proportion of BeThere intervention that could be explained by its effect on changes in caregiver wellbeing, caregiver distress, caregiver stress, and parenting. To quantify the magnitude of mediation, the study estimated the proportion of the effect mediated by caregiver wellbeing, caregiver distress, caregiver stress, and parenting ($NIE/[NDE + NIE]$). All analyses will be estimated using bootstrapping (500 replications) to recover the correct SEs for direct and indirect effects. Results are presented as coefficients and 95% confidence intervals (see appendix).

[figure not shown]
[figure not shown]

Figure 6 Primary mediation pathways

To assess the effect of group cohesion among beneficiaries in the BeThere intervention group on caregiver wellbeing and distress

First, we will examine the correlations among midline and endline group cohesion values with endline and follow-up caregiver wellbeing, stress, and distress.

We will use a structural equation model (SEM) to estimate the indirect effect of the BeThere intervention on caregiver outcomes through group cohesion. The model will specify caregiver wellbeing, caregiver stress, and caregiver distress at endline and follow-up as the outcomes using a similar method to that described above.

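### Objective 4 has no baseline-adjusted analysis of cohesion against caregiver outcomes among BeThere participants: the first step is unadjusted correlations, one set of them within a single visit

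*SAP*

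**What the plan says.** SAP Section 8 words the secondary objective as an effect within one arm: "To assess the effect of group cohesion among beneficiaries in the BeThere intervention group on caregiver wellbeing and distress". Section 27a, under Mediation Analyses, gives it two steps.

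- Step one: "First, we will examine the correlations among midline and endline group cohesion values with endline and follow-up caregiver wellbeing, stress, and distress". No covariate, test or clustering term is attached.
- Step two: "We will use a structural equation model (SEM) to estimate the indirect effect of the BeThere intervention on caregiver outcomes through group cohesion". The outcomes are wellbeing, stress and distress at endline and follow-up, "using a similar method to that described above". The text of that earlier method (the child-wellbeing model) names no baseline covariate.

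Section 26 sets what is available. For the exposure, "Group cohesion was assessed at midline, endline, and follow up", so there is no baseline cohesion. For the outcomes, "Caregiver psychological distress was assessed at baseline, midline, endline, and follow up" and "Caregiver psychosocial wellbeing was assessed at baseline, midline, endline, and follow up"; caregiver stress has the same four visits. Sections 15 and 26 restrict the midline visit to the BeThere arm.

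**The concern.** Cohesion is a caregiver's own rating of the group, given after entry. A caregiver who is less distressed at entry may rate the group more warmly and also be less distressed ten or twenty weeks later. That alone produces a correlation between cohesion and outcome. Baseline distress, stress and wellbeing are collected, so the measured part of this confounding can be removed.

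One set of correlations has a second problem. Endline cohesion and endline outcome are two self-reports from the same assessment, so any passing mood or response style on that day enters both.

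At stake is how the secondary objective is answered. It asks about an effect, and an unadjusted positive correlation is easily read as support for one.

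**Working it through.** **1. Which visit pairs are examined.** Two cohesion visits (midline, endline) times two outcome visits (endline, follow-up) give four pairs per outcome. In three, cohesion comes first: midline-endline, midline-follow-up and endline-follow-up. In one, endline-endline, both come from the same visit.

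**2. Is unadjusted the right reading?** The SAP states adjustment where it intends it. Section 27a adjusts the primary model for the baseline parenting score and, for relations among mediators, specifies partial correlations that account for allocation. The cohesion sentence has no such qualifier.

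**3. Number of caregivers.** Section 11 targets 960 caregivers and allows for 10% attrition; Section 22 gives 1:1 allocation. 960 / 2 = 480, and 480 × 0.9 = 432 BeThere caregivers. Section 11 gives 40 intervention groups, so 432 / 40 = 10.8 analysed per group. The SAP states no figure for the cohesion analysis to reproduce.

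**4. Spurious correlation with no cohesion effect.** If baseline mood is the only link, r(cohesion, outcome) = r(baseline, cohesion) × r(baseline, outcome). Both inputs are assumptions. With r(baseline, outcome) = 0.5:

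| r(baseline, cohesion) | spurious r | chance of p < 0.05, n = 432 |
|---|---|---|
| 0.1 | 0.05 | 18% |
| 0.2 | 0.10 | 55% |
| 0.3 | 0.15 | 88% |

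The last column uses Fisher's z, with mean atanh(r) × √429 compared with 1.96. For r = 0.10 this is 0.1003 × 20.71 = 2.08. Over a wider range (r(baseline, cohesion) 0.2 to 0.4, r(baseline, outcome) 0.3 to 0.6), the spurious r runs from 0.06 to 0.24 and the chance from 24% to above 99%. In simulation, partialling out the baseline score returns the rate to about 5%. That follows by construction, because baseline is the only confounder simulated.

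**5. The same-visit pair.** Add a shared reporting component with loading 0.3 on each measure (9% of each variance), with r(baseline, cohesion) = 0.3 and r(baseline, outcome) = 0.5. Raw r = 0.3 × 0.5 + 0.09 = 0.24. Baseline-partial r = 0.09 / √(0.91 × 0.75) = 0.109, still significant in about 62% of samples. Baseline adjustment does not repair this pair.

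**6. Does baseline adjustment repair the midline pairs?** Not fully. Midline cohesion is reported at the same visit as midline mood. Assume mood correlates 0.5 between any two visits, midline mood correlates 0.2 with midline cohesion, and cohesion has no effect. Then r(cohesion, outcome) = 0.2 × 0.5 = 0.10 and r(baseline, cohesion) = 0.2 × 0.5 = 0.10. The baseline-partial r is (0.10 − 0.10 × 0.5) / √(0.99 × 0.75) = 0.05 / 0.862 = 0.058, significant in about 22% of samples. Adjusting also for midline mood removes this remainder under these assumptions.

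**7. Group clustering.** Assume intraclass correlations of 0.2 for cohesion and 0.05 for the outcome. The variance of the correlation rises by about 1 + (10.8 − 1) × 0.2 × 0.05 = 1.10. A nominal 5% test would then reject in about 6%. Clustering is a minor part of the problem; confounding is the main part.

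**The case against.** The strongest reply is that the correlations are a preliminary look. The SAP attaches no test, decision rule or conclusion to them, and an estimating model follows. Unadjusted associations before a model are ordinary practice. This stands: a reader might infer that the conclusion on objective 4 will rest on these correlations, but the SAP does not say so. The significance rates above likewise presuppose a test that the SAP does not specify for this step.

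The reply falls short because the second step has a different target. It estimates how much of BeThere's effect passes through cohesion, which is not the cohesion-outcome association among beneficiaries, and its text names no baseline covariate. The path diagrams are missing from the copy reviewed, so they may show more.

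Two other stronger readings are not supported. One is that the plan treats members of the same BeThere group as independent. The text is silent on standard errors here, and the group identifier is in the planned dataset. The other is that the second model cannot be run at all, so that only the correlations remain. Only the midline visit is expressly limited to the BeThere arm; the Section 26 schedule lists endline and follow-up cohesion without an arm restriction.

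It is also fair to say that spurious correlations of 0.05 to 0.15 are weak (0.25% to 2.25% of variance), and that baseline adjustment alone does not settle the matter, as working step 6 shows.

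**Conclusion.** The point holds as a modest, inexpensive improvement. An objective worded as an effect is paired with unadjusted correlations as its first step, one of the four visit pairs is same-visit, and no listed analysis supplies a baseline-adjusted cohesion-outcome association among beneficiaries. It does not show that the plan would draw a false conclusion.

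The size is unknown. The figures of 0.05 to 0.15 rest on assumed correlations, and only the sample size, group count and attrition come from the SAP. Adjustment cannot remove unmeasured confounding, so even the improved analysis supports an association and not an effect. The primary outcome and the effectiveness comparisons are untouched.

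**What to change.** In Section 27a, under the cohesion objective, specify within the BeThere arm:

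- Regress endline and follow-up wellbeing, distress and stress on midline cohesion, and follow-up outcomes on endline cohesion.
- Adjust each model for the baseline value of the same outcome and for community, and account for clustering by BeThere group and household.
- Add a sensitivity model that also adjusts for the outcome at the visit where cohesion was measured (midline or endline). Keep it as a sensitivity analysis, because it could remove part of a real effect already present at that visit.
- Report the raw correlations, and any endline-endline correlation, as descriptive only.
- Word the results as associations.

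The cost is SAP wording and a few regressions on variables already in the planned dataset. Section 14 places cohesion analyses after the effectiveness analyses, so masking is unaffected. Estimates are likely to be smaller than the raw correlations suggest, with slightly wider intervals.

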14. Timing of final analysis

All analyses will be conducted after completion of data collection for the trial. The statistician and PI will be masked to study condition during data collection, cleaning, and the primary effectiveness analyses. Secondary analyses examining mediators that relate to intervention group characteristics (e.g., BeThere Mechanism of Action, Group Cohesion) or require analysis of intervention midline assessment data will be conducted after effectiveness analyses are finalized to preserve masking.

15. Timing of outcome assessments

Data used for this study will be collected by research assistants at baseline, midline (BeThere session 5), endline (within 2-3 weeks following session 9 or approximately 10-12 weeks post-enrollment), and follow-up (12 weeks after completion of the final session or approximately 22 weeks post-enrollment). The midline assessment was only administered to the experimental (i.e., BeThere) group and not to the waitlist control group.

SECTION 4: STATISTICAL PRINCIPLES

16. Level of statistical significance

A significance level of $\alpha=0.05$ will be applied.

17. Adjustments for multiplicity

We do not plan to adjust for multiple testing.

18. Confidence intervals

Results will be presented as coefficients and 95% CIs.

19. Adherence and protocol deviations

Participant adherence to the intervention will be measured using intervention session attendance records. Completion of the intervention will be defined as having attended seven or more sessions. We will report the mean (SD) and median (IQR) number of sessions attended in the BeThere group.

Facilitator fidelity to the intervention will be measured using a fidelity checklist. We will report the mean (SD) and median (IQR) scores on the fidelity checklist as an indicator of trial implementation quality.

Any major deviations from the protocol will be reported in the main outcomes paper.

20. Analysis populations

The primary analysis will be conducted on the intent-to-treat sample, meaning that all participants will be included and analyzed as randomized. No enrolled participants were excluded from the main analytic sample. We will also conduct a per protocol analysis including waitlist control participants who completed all assessments and did not participate in any BeThere intervention components and only BeThere intervention participants who completed seven or more intervention sessions and did not drop out of the study.

SECTION 5: TRIAL POPULATION

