- **Mechanisms of Action:** Total score on a 5-item measure developed to assess hypothesized mechanisms for the BeThere intervention (e.g., relaxation techniques, stress and anger management, positive parenting practices). Mechanisms of action were assessed at baseline, midline, endline, and follow up.
- **Caregiver psychological distress (see above)**
- **Caregiver stress (see above)**
- **Caregiver wellbeing (see above)**
- **Parenting (see above)**

Implementation variables

- **Attendance:** Number of sessions attended (participant-level; range: 0-9)
- **Facilitator competence:** ENACT score (12 of 15 items) measured post-training/pre-implementation and during training. We will operationalize facilitator competence as the % of harmful (item score=1) and % of not harmful (item score=3-4) behaviors observed
- **Intervention fidelity:** Total score on BeThere fidelity tool (8-items) assessing the number of intervention components adequately implemented per session (Range: 72-216)

Study outcome measures and timepoints

Measures	Baseline	Randomisation	Midline*	Endline	Follow up	Ongoing
Caregiver						
Parenting (BPS)	X			X	X	
Psychological Distress (K10)	X		X	X	X	
Caregiver stress	X		X	X	X	
Psychosocial wellbeing (WEMWBS)	X		X	X	X	
Child wellbeing (KINDL)	X			X	X	
Group cohesion (GCS)			X	X	X	
Mechanisms of action (MOA)	X		X	X	X	
Child						
Parenting (BPS – Child Version)	X			X	X	
Psychosocial wellbeing (KINDL)	X			X	X	
Randomisation		X				
Adverse events						X

*Midline assessments administered to BeThere study arm only

27a. Analysis methods

Data Management

We will prepare both a long and wide final dataset. The long dataset will include a separate observation for each assessment. The wide dataset will include one observation per individual with variables for each assessment period. The final dataset will include the following variables:

- Community identifier
- Household identifier
- Individual identifier (caregivers, child)
- Allocation [masked: will be coded 0 or 1 without a label until primary analyses are complete]
- BeThere group number/identifier
- Assessment number/time point
- Assessment date
- Caregiver age
- Child age
- Caregiver gender
- Number of caregivers in the household
- Caregiver-reported parenting items and total score
- Child-reported parenting items and total score
- Caregiver psychological distress items and total score
- Caregiver stress items and total score
- Caregiver wellbeing items and total score

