Appendix 1. Table Shells

1. Study variables (Section 25a)

Variable name	Variable description	Variable type	Variable coding/values
id	Unique ID. Each participant possesses a unique ID that indicates the community (1 st digit), family code (2 nd -4 th digit), and the participant type (5 th digit: female caregiver '1', male caregiver '2', or child '3').	Nominal	11111-99999
int_location	Community (numeric identifier) of residence	Nominal	1: Tbek 2: Ghoi 3: Sukzero/Taragok 4: Malou/Anglican Church/Lenguet 5: Pariak
household	Household (numeric identifier).	Nominal	1-9999
id_fv	Caregiver ID (numeric identifier)	Nominal	1-9999
Id_ch	Child ID (numeric identifier)	Nominal	1-9999
allocation	Study condition (BeThere vs. waitlist) Note: the labelling will not be revealed until after primary analyses have been completed	Nominal	0: TBC 1: TBC
betheregrp	BeThere group number Note: if waitlist groups are not enumerated then do not include this variable in the dataset until primary analyses have been completed	Nominal	1-99
assessment	Assessment number Note: do not include midline data until the primary analyses have been completed	Ordinal	0: Baseline 1: Midline 2: Endline 3: Follow up
assessweeks	Number of weeks since enrolment	Continuous	Time since baseline (in weeks)
assessdate	Date of the assessment	Date	DD-Mon-YY
cg_gender	Gender (caregiver)	Nominal	1: Female 2: Male
num_caregivers	Number of caregivers in the household	Continuous	1-2
ic_age_t1	Child age (in years; caregiver-reported)	Continuous	3-14
parenting	Total score on parenting measure (caregiver reported)	Numeric, continuous	24-120
parenting_01, parenting_02, parenting_03, parenting_04, parenting_05 (reverse), parenting_06, parenting_07,	Item score on parenting measure (caregiver-reported)	Numeric, continuous	1-5

parenting_08, parenting_09, parenting_10, parenting_11, parenting_12, parenting_13, parenting_14, parenting_15 (reverse), parenting_16, parenting_17 (reverse), parenting_18 (reverse), parenting_19 (reverse), parenting_20 (reverse), parenting_21, parenting_22, parenting_23, parenting_24			
parenting_warmth_cg	Total score on parenting warmth subscale (caregiver reported)	Numeric, continuous	17-85

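### The group cohesion SEM targets an indirect effect of BeThere for which the SAP defines no waitlist comparator, while objective 4 asks a within-arm question

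*SAP*

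**What the plan says.** Section 8 gives the secondary objective, and Section 27a repeats it as the heading of the cohesion analysis: "To assess the effect of group cohesion among beneficiaries in the BeThere intervention group on caregiver wellbeing and distress". Two steps follow in Section 27a. The first correlates midline and endline cohesion with endline and follow-up wellbeing, stress and distress. The second is the model: "We will use a structural equation model (SEM) to estimate the indirect effect of the BeThere intervention on caregiver outcomes through group cohesion". It takes wellbeing, stress and distress at endline and follow-up as outcomes and borrows the approach of the main mediation model, which reports total, natural direct and natural indirect effects with bootstrapped standard errors.

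On measurement, Section 26 says "Group cohesion was assessed at midline, endline, and follow up", so there is no baseline value. Section 15 says of midline: "The midline assessment was only administered to the experimental (i.e., BeThere) group and not to the waitlist control group". The footnote to the measures table repeats this ("Midline assessments administered to BeThere study arm only") and says nothing about the arm for endline or follow-up. Section 14 defers analyses of "mediators that relate to intervention group characteristics (e.g., BeThere Mechanism of Action, Group Cohesion" and similar variables until the effectiveness analyses are final, to preserve masking. Appendix 1 gives the cohesion total a range of 7 to 35, with no code for a caregiver who has no group.

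**The concern.** The question and the model do not match. Objective 4 concerns people who sat in a BeThere group. It asks whether those who report more cohesion do better, and the waitlist arm plays no part in that. The SEM asks how much of the effect of allocation passes through cohesion. That quantity is the product of two paths: allocation to cohesion (a) and cohesion to outcome (b). The a path is a difference between arms, so cohesion must have a meaningful value in both.

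This SEM is the only model specified for the only secondary objective, and Section 1 assigns the mediator results to a second manuscript. If it is run as written, it will either fail or return a number that reflects a coding decision and is read as a causal mechanism.

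**Working it through.** The SAP gives no figure for this analysis, so there is nothing to reproduce. The check is whether the planned quantity is identified.

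**Step 1: cohesion observed in the BeThere arm only.** This holds at midline by the SAP's own statement. Among caregivers with a cohesion value, allocation is constant (variance 0), and the design matrix [1, allocation, cohesion] has rank 2 of 3. Neither the a path nor the direct effect can be estimated. Outcome data from the waitlist arm do not help: they identify the total effect, which equals direct effect + a×b, but not how it divides.

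**Step 2: waitlist cohesion set to a constant c.** The SAP does not plan this. It is one way to make the model run. Then a = (mean BeThere cohesion − c), b is the slope within the BeThere arm, and the indirect effect is b × (mean − c). Each one-point change in c moves the indirect effect by b, whatever the data say.

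Illustration: one simulated data set with 956/2 = 478 caregivers per arm. Assumed values are BeThere cohesion with mean 26 and SD 4, a within-arm slope of 0.3, a treatment effect of 2 and a residual SD of 8. In the simulated data the mean cohesion was 25.72, b = 0.256 and the total effect was 2.13.

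| c | a | Indirect effect | Direct effect | Proportion mediated |
|---|---|---|---|---|
| 0 | 25.72 | 6.59 | -4.46 | 3.09 |
| 7 | 18.72 | 4.80 | -2.66 | 2.25 |
| 14 | 11.72 | 3.00 | -0.87 | 1.41 |
| 21 | 4.72 | 1.21 | 0.92 | 0.57 |
| 26 | -0.28 | -0.07 | 2.20 | -0.03 |
| 35 | -9.28 | -2.38 | 4.51 | -1.11 |

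The slope b is 0.256 in every row. It is the only part that the data determine, and it is the quantity objective 4 asks about.

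**Step 3: is a within-arm analysis feasible?** Section 11 gives 40 intervention groups and 10% attrition. Then 478 × 0.9 = 430 caregivers, and 430/40 = 10.75 per group if all 40 are BeThere-arm groups. With effective n = 430/[1 + (10.75 − 1) × ICC], the detectable correlation at two-sided 0.05 and 80% power is tanh[(1.96 + 0.84)/√(effective n − 3)]. The ICC and the power are assumptions.

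| ICC | Effective n | Detectable correlation |
|---|---|---|
| 0 | 430 | 0.135 |
| 0.05 | 289 | 0.164 |
| 0.10 | 218 | 0.189 |
| 0.20 | 146 | 0.230 |
| 1 (purely group-level) | 40 | 0.431 |

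If the 40 groups span both arms, groups are twice as large (21.5) and precision is lower. At ICC 0.20 the design effect is 1 + 20.5 × 0.20 = 5.10, the effective n is 430/5.10 = 84, and the detectable correlation is about 0.30.

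**The case against.** A reader might infer that cohesion is never measured in the waitlist arm. The SAP does not establish this. The restriction is explicit for midline only. The measures table lists cohesion at endline and follow-up without naming an arm, and the variable list in Section 27a marks attendance as BeThere-only but not cohesion. Appendix 1 leaves open whether waitlist caregivers are assigned to groups ("if waitlist groups are not enumerated then do not include this variable in the dataset until primary analyses have been completed"). The passage in Section 14 does not settle it either. It puts cohesion beside Mechanisms of Action, which is measured at baseline, before randomisation, and so in both arms. All of this stands, and the point is limited accordingly. It does not rescue the SEM, because the SAP describes no group that a waitlist caregiver would have attended and could rate, and the midline contrast remains absent in any case.

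A reader might also infer that objective 4 goes wholly unanswered. That is too strong. The planned correlations bear on it, and so does the cohesion-to-outcome path of the SEM. However, the correlations carry no restriction to the BeThere arm, no baseline adjustment and no allowance for shared groups.

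Finally, the filled-in values in the working are hypothetical, since the SAP proposes no such coding. They show what the estimate would depend on, not what the analyst intends.

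**Conclusion.** The point holds for the indirect effect. At midline the allocation-to-cohesion path has no comparator. At endline and follow-up the SAP defines neither who is rated nor what a waitlist rating would mean. The indirect effect and the proportion mediated are therefore not identified, or depend entirely on the value assigned to waitlist caregivers. This conclusion rests on no assumed figure. The simulated range of 4.80 to -2.38 across the 7 to 35 scale is an illustration under stated assumptions. The within-arm slope remains estimable, with precision that depends on the unknown ICC and on how the 40 groups divide between arms.

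The point does not touch the analysis of the primary outcome. There is also a small mismatch of scope: objective 4 names wellbeing and distress, while the SEM adds stress.

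**What to change.** In Section 27a:

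- Delete the indirect effect of BeThere through group cohesion, with its proportion mediated.
- State who completes the cohesion scale at endline and follow-up and, if waitlist caregivers do, which group they are rating.
- Specify a mixed model in the BeThere arm only: endline and follow-up wellbeing and distress (and stress, if kept) on cohesion measured earlier, adjusted for the baseline outcome, with random intercepts for BeThere group and household.
- Restrict the preliminary correlations to the BeThere arm and label them descriptive.
- Report the result as a non-randomised within-arm association.

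Splitting cohesion into a group mean and an individual deviation is optional.

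The cost is SAP wording. Cohesion scores, the BeThere group identifier, the household identifier and baseline outcomes are already in the planned dataset. The price is that the cohesion claim becomes associational. The change should be made before the unmasked secondary analyses begin.
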